1 BACKGROUND/SCIENTIFIC RATIONALE

- Prescription opioid use by adolescents and young adults aged 12-25 years increases their risk of prescription opioid misuse.^{1,2} Leftover opioids from prior prescriptions for acute pain are a key driver of this misuse. As such, it is crucial to ensure that quantities in opioid prescriptions match the needs of adolescents and young adults.³
- Several prior studies have utilized default dosing settings to reduce the size of opioid prescriptions written to adults. In a study in the University of Pennsylvania adult emergency department, the default quantity of oxycodone-acetaminophen tablets in the electronic health record (EHR), was set to 10 tablet; providers could override the settings and prescribe other quantities at their discretion. After this intervention was implemented, the percentage of Percocet prescriptions written for 10 tablets increased from 20.6% to 43.3%, demonstrating that EHR default settings can affect opioid prescribing.⁴
- However, no study has utilized default dosing settings to promote appropriate opioid prescribing to adolescents and young adults. Furthermore, no study of default dosing settings to date has chosen the level of these settings based on evidence on patient need.
- In this study, we will collect data on patient-reported post-surgical opioid consumption among adolescents and young adults undergoing tonsillectomy at the University of Michigan. These data will inform the design of a default dosing setting intervention. We will assess whether implementation of the intervention is associated with changes in opioid prescribing and consumption. Additionally, we will assess for potential unintended consequences, including worsened patient satisfaction, pain control, sleep, anxiety, depression, and functioning; or increased requests for refills or return visits for uncontrolled pain.
- The research team has significant experience with collecting data on patient-reported opioid consumption and patient-reported outcomes such as pain control, as well as with developing evidence-based opioid prescribing guidelines.

2 OBJECTIVES

- To evaluate changes in opioid prescribing, consumption, patient-reported outcomes, and health care utilization after implementation of a behavioral intervention using evidence-based default dosing settings for opioid prescriptions to adolescents and young adults undergoing tonsillectomy

3 EXPECTED RISKS/BENEFITS

- There are no expected direct benefits to subjects. The expected risks for subjects are no more than minimal.
 - The most likely risk to study subjects is the time burden associated with completing the surveys.
 - There is a possible risk of breach of confidentiality, although the study team will take measures to prevent such breaches.
 - There is a possible risk of worsened pain control, although literature suggests this is unlikely. For example, an evidence-based opioid prescribing guideline was instituted for University of Michigan patients undergoing gallbladder removal in 2015 and 2016. Prior to institution of this guideline, patients received an average of 50 pills of hydrocodone/acetaminophen but only consumed 6. Institution of the guideline was associated with a 63% reduction in prescription size without increasing the need for opioid prescription refills.⁵
 - There is a possible risk that the intervention could cause depression or suicidal ideation, or that increased opioid misuse could occur. Prior studies evaluating interventions to reduce opioid prescribing for acute pain have not evaluated these outcomes, so these risks remain theoretical. However, the primary mechanism of these unintended consequences would be worsened pain control, which is unlikely given the reasons above.
- Future patients and society may benefit from the research results. The default setting intervention could be broadly applicable to other procedures and conditions, and could also be readily scalable to other institutions due to its low cost of implementation. If this intervention is successful in limiting excessive opioid prescribing to adolescents and young adults, widespread adoption could reduce the number of unused opioids available for misuse and diversion in adolescents and young adults.

4 ELIGIBILITY

- Subject population: Adolescents and young adults undergoing tonsillectomy
- Inclusion criteria
 - Adolescents and young adults aged 12-25 years will be eligible to be recruited if they undergo palatine tonsillectomy with or without adenoidectomy on the pediatric or general otolaryngology service of the University of Michigan Medical School, and if they are not:
 - Patients in foster care or patients with a legal guardian
 - Patients with developmental delays, such as autism
 - Patients who are non-English speaking
 - Patients with recent suicidal ideation
 - Patients undergoing emergent tonsillectomy

- Exclusion criteria for primary analysis analyzing prescribing
 - Patients who were approached for consent but declined
 - Patients with prescription opioid use prior to surgery
 - Patients undergoing additional major procedures at the same time as tonsillectomy
 - Patients enrolled in another study
 - Patients who are not prescribed opioids post-operatively
 - Patients who are enrolled in the “M-POP” pathway, which includes education about pain management and a small initial opioid prescription (10 doses)
 - Patients with hospitalization with length of stay > 1 day after surgery
- Additional exclusion criteria for secondary analysis examining patient-reported outcomes through surveys
 - Patients who were not reached for consent
 - Patients who do not complete the baseline and post-operative day 14 surveys
- Inclusion of vulnerable populations: The purpose of this study is to evaluate an intervention on opioid prescribing to adolescents and young adults. As such, minors must be included in the study.

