5 SUBJECT ENROLLMENT

- Screening
 - Patients scheduled to undergo tonsillectomy during the study period will be identified using the surgical scheduling system and screened to against age criteria.
- Enrollment
 - The study team will recruit all eligible patients. Recruitment will occur over the phone or in-person during the 14-day period before the day of surgery for patients undergoing tonsillectomy at C.S. Mott Hospital or University Hospital. A study team member will e-mail patients who enroll with a PDF version of the consent and a pain journal they can print to record the number of opioid doses consumed. For those patients who cannot be contacted, in-patient recruitment will occur pre-operatively on the day of surgery. A study team member will provide patients who enroll with a paper pain journal they can use to record the number of opioid doses consumed.
 - Recruitment will occur over the phone during the 14-day period before the day of surgery for patients undergoing tonsillectomy at the Brighton Center for Specialty Care or Livonia Center for Specialty Care. A study team member will e-mail patients who enroll with a PDF version of the

consent and a pain journal they can print to record the number of opioid doses consumed.

- Incentives
 - Subjects will be compensated \$10 for completing the baseline survey, \$10 for completing all 13 daily post-operative surveys, and \$10 for completing the final survey on post-operative day 14. Subjects will be compensated based on the number of sets of surveys completed (e.g., if they complete the baseline and post-operative surveys, they will receive \$20). Compensation will be mailed after post-operative day 14.

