6 STUDY DESIGN AND PROCEDURES

- Study design
 - The study will use a difference-in-differences design in which changes before and after the intervention will be compared between a treatment group and a control group.
 - The treatment group will include all patients undergoing tonsillectomy at C.S. Mott Hospital by a pediatric otolaryngology faculty member at the University of Michigan.
 - The control group will include all patients undergoing tonsillectomy at University Hospital, Brighton Center for Specialty Care, or Livonia Center for Specialty Care by a general otolaryngology faculty member at the University of Michigan.
- Data collection procedures throughout the study
 - There will be three sets of surveys: a baseline survey, daily surveys on post-operative days 1-13, and a final survey on post-operative day 14. Post-operative surveys will be sent to all patients who enroll, including those who are not prescribed opioids post-operatively. These patients will not be included in the primary or secondary analysis but will be analyzed in a separate study examining pain recovery without opioids.
 - Baseline survey: Patients will be asked to complete a 10-15 minute survey assessing demographics, reason for tonsillectomy, current pain, chronic pain, history of opioid use, history of opioid misuse, family chronic opioid use, depression, substance use disorders, anxiety, sleep, and global health. Patients will be e-mailed a link to the baseline survey upon enrollment; for patients who cannot receive e-mail links, the survey will be administered over the phone. For patients at Mott or University Hospital recruited in-person, the baseline survey will be administered by a study team member in-person through Qualtrics on a tablet. Patients sent the baseline survey who do not complete it before surgery will be contacted via e-mail or by phone to remind them or approached in-person to complete it through Qualtrics on a tablet. If patients are contacted by phone, they will be given the option to complete the survey over the phone.

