- Daily surveys: At 12:01 am on post-operative days 1 through 13, patients will be e-mailed a daily link to complete a 1-minute online Qualtrics survey in which pain and opioid consumption over the prior 24 hours will be assessed. The post-operative day 7 survey will be similar except that it will include additional questions assessing pain over the prior 7 days. Patients who cannot receive e-mail links will not be sent daily surveys. E-mail or telephone follow-up will not occur for the daily surveys on post-operative days 1-13.
 - Final survey: on post-operative day 14, patients will be e-mailed a link to complete a 10-15-minute online Qualtrics survey assessing pain control, opioid use, opioid disposal, opioid misuse, acetaminophen/ibuprofen use, depression, anxiety, sleep, and health care utilization during the 14 days after surgery, including refills and visits to the emergency department or primary care for pain. Patients who cannot receive e-mail links will be called and the survey will be administered over the phone. Patients may be contacted via e-mail or by phone to remind them to complete surveys. If patients are contacted by phone, they will be given the option to complete the survey over the phone.
 - DataDirect and MiChart will be queried to determine opioid use prior to the day of surgery based on the admission history and physical, patient demographics, the dosing parameters of post-operative opioid prescriptions, the number of return visits for pain at the University of Michigan in the 14 days after surgery, and the number of opioid refills in the 14 days after surgery.
- Timeline
 - The pre-intervention period will start on October 1, 2019 and end September 30, 2020; the months of April and May 2020 will be excluded as elective surgeries were scaled down owing to the COVID-19 pandemic. The intervention will be implemented on October 1, 2020. The post-intervention period will start October 1, 2020 and end on July 31, 2021.
 - Nature of intervention
 - Currently, pediatric otolaryngology attendings and their residents use a MiChart tonsillectomy orderset with three options: patients < 12 years, patients ≥12 years, and M-POP. Under the orderset for patients ≥12 years, the default is currently 30 doses, consistent with the current departmental prescribing standard (see MiChart screenshot below).
 - During the pre-intervention period, no changes will be made to the default number of doses or any other dosing parameter.

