10 STATISTICAL CONSIDERATIONS

- Outcomes in primary analysis
 - Number of doses in the discharge opioid prescription
 - Proportion of patients in which the number of doses in the discharge opioid prescription equals the number of doses in the new default settings
 - Proportion of patients prescribed opioids at discharge
 - Proportion of patients prescribed opioids at discharge who had at least one opioid prescription refill from UM during the two weeks after surgery
 - Proportion of patients who saw a UM provider in an office due to pain during the two weeks after surgery

- Proportion of patients with at least one emergency department visit or hospitalization at UM for pain during the two weeks after surgery
- Additional outcomes in secondary analysis (based on data from the final post-operative day 14 survey)
 - Overall satisfaction with pain control during the two weeks after surgery (scale of 1-10)
 - Proportion of patients who reported that their pain was well-controlled
 - Proportion of patients whose overall pain control was rated as much worse or worse than expected
 - Proportion of patients whose pain has resolved by day 14 after surgery
 - Pain score over the past 7 days at its worst (scale of 0-10)
 - Pain score over the past 7 days on average (scale of 0-10)
 - Number of opioid doses taken during the two weeks after surgery
 - Proportion of patients with leftover doses of opioids
 - Proportion of patients with leftover doses who disposed of them
 - Proportion of patients who misused opioids belonging to others at least once during the two weeks after surgery
 - Proportion of patients who misused their own opioids at least once during the two weeks after surgery
 - PHQ-8 score (depression)
 - Score on PROMIS Pediatric Anxiety – Short Form 8a
 - Score on PROMIS Sleep Disturbance – Short Form 8a
 - Proportion of patients who saw their primary care provider (or a colleague) in the office due to poorly controlled pain at least once during the two weeks after surgery
 - Proportion of patients who visited an urgent care center due to poorly controlled pain at least once during the two weeks after surgery
 - Proportion of patients who visited a retail clinic due to poorly controlled pain at least once during the two weeks after surgery
 - Proportion of patients who went to an emergency department and/or were hospitalized due to poorly controlled pain at least once during the two weeks after surgery

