- Data from the daily surveys will be used to assess whether daily opioid consumption reports matches the consumption reported on the final post-operative day 14, and will also be analyzed in a separate study assessing the trajectory of pain and opioid use after tonsillectomy.
- We will fit linear or logistic regression models assessing outcomes as a function of an indicator of post-intervention status, an indicator of treatment group status, and its interaction, controlling for covariates such as demographics (e.g., age, sex) and baseline co-morbidities (e.g., depression, anxiety). We will graphically and statistically assess the comparability of pre-intervention monthly trends in outcomes between the treatment and control groups.

- We hypothesize that there will be no change in outcomes in the control group (i.e., that the post-intervention trend in outcomes in the control group will be an extension of the pre-intervention trend in outcomes). In contrast, we hypothesize that the number of doses and opioid consumption will drop in the treatment group after the intervention; that the proportion of patients with prescriptions concordant with the new defaults will increase after the intervention; and that there will be no change in balancing measures such as pain control or depression.
- Sensitivity analyses
 - Statistical modeling: we will explore whether results change when replacing the indicator of treatment group status with a vector of fixed effects for the prescribing clinician, and will explore the feasibility of using an interrupted time series approach instead of a difference-in-differences approach.
 - We will determine whether any otolaryngology residents wrote opioid prescriptions for both a pediatric otolaryngology and general otolaryngology patients in the post-intervention period, and exclude data from any such residents from the analysis
 - We will exclude opioid prescriptions written for patients of the chief of pediatric otolaryngology, who will be involved in setting the new defaults
- Subgroup analysis will occur by age group (ages 12-17 years vs 18 and older), gender, payer type (private/public), and baseline co-morbidities (e.g., depression and anxiety).
- We will separately analyze data from pediatric otolaryngology patients undergoing surgery outside of Mott and general otolaryngology patients undergoing surgery at Mott to assess for any spillover effects.

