- Sample size: Based on historical UM data, we estimate that there will be 113 patients in the treatment group and 85 in the control group for the primary analysis (total 198). If 65% consent to complete the surveys, then there will be 74 and 55 patients in the treatment and control groups for the secondary analysis, respectively (total 129).

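### The proportion of patients prescribed opioids at discharge is a primary-analysis outcome, yet patients not prescribed opioids are excluded from that analysis

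*Combined protocol and SAP*

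**What the plan says.** All references are to the combined protocol and SAP.

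- Section 4, in the exclusions for the primary analysis of prescribing, lists "Patients who are not prescribed opioids post-operatively".
- Section 6 says that enrolled patients not prescribed opioids still receive the surveys. It then states: "These patients will not be included in the primary or secondary analysis". They go instead to a separate study of recovery without opioids.
- Section 10 lists six primary-analysis outcomes. One is "Proportion of patients prescribed opioids at discharge", with no denominator of its own. Another is "Number of doses in the discharge opioid prescription". The refill outcome is expressly limited to patients prescribed at discharge.
- Section 10 applies one approach to all of them: "We will fit linear or logistic regression models assessing outcomes" on period, group and their interaction.
- Section 6 draws "the dosing parameters of post-operative opioid prescriptions" from the chart. No section defines a post-operative prescription in relation to a discharge prescription.

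**The concern.** An analysis set chosen by whether an opioid was prescribed cannot, in general, measure how often opioids are prescribed. The exclusion appears in two sections, so it does not look like a stray line.

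This is the only listed outcome on whether a patient is prescribed an opioid at all. The dose and default-concordance outcomes describe prescriptions that were written. Computed as the text directs, this outcome could yield a zero, or a small difference, produced by the exclusion. The risk is that such a result is reported as evidence that the new default did not change whether opioids were prescribed.

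**Working it through.** **The plan's own figures.** Section 10 says "we estimate that there will be 113 patients in the treatment group and 85 in the control group for the primary analysis": 113 + 85 = 198, as stated. At 65% consent, 0.65 × 113 = 73.45, 0.65 × 85 = 55.25 and 0.65 × 198 = 128.7, which agree with the stated 74, 55 and 129 to within one patient. The plan gives no prescribing rate, so there is no planned value of this outcome to reproduce.

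**Reading 1: post-operatively means at discharge.** Everyone left in the set has the outcome. The difference-in-differences is (100% − 100%) − (100% − 100%) = 0. Least squares on 198 ones with the group-by-period interaction returns 0, and the logistic fit does not converge because the outcome does not vary. No assumption is needed.

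**Reading 2: post-operatively is wider.** Let p be the true proportion prescribed at discharge among otherwise eligible patients, and q the share of the rest who count as prescribed post-operatively in some other way. Neither is in the documents; every value below is an assumption. After the exclusion the observed proportion is

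f(p, q) = p / (p + (1 − p)q).

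With control unchanged and q equal in all cells, a true fall of 10 points from baseline p0 appears as f(p0 − 0.10, q) − f(p0, q). For example, at p0 = 0.90 and q = 0.20: 0.80/0.82 is the value for q = 0.10, while q = 0.20 gives 0.80/0.84 − 0.90/0.92 = 0.9524 − 0.9783 = −2.6 points.

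| Assumed baseline | q = 5% | 10% | 20% | 50% | 90% |
|---|---|---|---|---|---|
| 95% | −0.6 | −1.2 | −2.4 | −5.5 | −9.2 |
| 90% | −0.7 | −1.3 | −2.6 | −5.8 | −9.3 |
| 80% | −0.9 | −1.7 | −3.1 | −6.5 | −9.5 |
| 30% | −6.2 | −9.7 | −12.6 | −12.8 | −10.5 |

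At baselines of 80% to 95%, half of the true change is recovered only once q reaches about 0.35 to 0.45. At a 30% baseline with q of 20% or more the change is overstated.

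**If q differs between cells.** With p = 0.90 throughout and q rising from 0.10 to 0.30 in treated patients only, 0.9/0.93 − 0.9/0.91 = −2.1 points with no true effect. With a true fall from 90% to 80% and q falling from 0.30 to 0.10, 0.8/0.82 − 0.9/0.93 = +0.8 points, the wrong sign.

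**Precision if the exclusion is lifted.** The expected estimate then equals the true change. The pre-period has 12 − 2 = 10 months and the post-period 10, so an even split gives cells of 113/2 = 56.5 and 85/2 = 42.5. For a true −20 points, p1 = p0 − 0.20, and the 95% half-width is 1.96 × √[p0(1 − p0)/56.5 + p1(1 − p1)/56.5 + 2p0(1 − p0)/42.5].

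- 95% baseline: 1.96 × √(0.235/56.5 + 0.095/42.5) = 15.7 points.
- 90% baseline: 1.96 × √(0.300/56.5 + 0.180/42.5) = 19.1 points.
- 80% baseline: 1.96 × √(0.400/56.5 + 0.320/42.5) = 23.7 points.

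If 198 is the count after the exclusion, the set grows. At 90% it becomes 198/0.9 = 220 and the half-width falls from 19.1 to 18.2.

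**The case against.** **The intended denominator can be inferred.** The refill outcome is restricted to patients prescribed at discharge, while this one says only patients, which suggests that a wider set was meant. That is a fair reading of intent, but Sections 4 and 6 forbid it as written. It points to a missing exemption and does not remove the contradiction.

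**The consequence is limited.** This is one of six primary-analysis outcomes. The intervention changes the default number of doses, and the hypotheses in Section 10 name doses, consumption, default concordance and balancing measures, not whether an opioid is prescribed. On Reading 1 the failure is also visible: every cell is 100%. All of this stands, and it limits the severity. It does not help on Reading 2, where the output looks like an ordinary estimate.

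**The attenuation is assumed.** A reader might infer that the estimate must be close to zero on any reading. The documents do not support that, because they give neither p nor q. If in-hospital orders counted, q could be near 1 and little would be lost. That fits poorly with setting up a separate study of patients without opioids, since few would then be excluded, but the text does not rule it out. At low baselines the bias can run the other way.

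**Conclusion.** The contradiction is real and should be fixed; it is confined to this one outcome. On the discharge reading the outcome carries no information, with no assumption needed. On a wider reading the analysis set is still selected on a variable tied to the outcome. What the estimate shows then depends on an unstated q: from 0.7 to 9.3 points of a true 10 at an assumed 90% baseline, with overstatement or a wrong sign possible in other circumstances. These figures rest on assumed p and q and an unchanged control group.

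A reader might also infer that the primary analysis as a whole fails, or that 198 is wrong. Neither follows. The dose, default-concordance and refill outcomes remain computable as written, and nothing in the documents shows the projected total to be in error.

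**What to change.** For this outcome only, lift the exclusion of patients not prescribed opioids and analyse it in all otherwise eligible tonsillectomy patients. Amend the Section 4 and Section 6 sentences to match, and define being prescribed opioids post-operatively in relation to being prescribed at discharge. The alternative is to drop the outcome, which costs nothing but leaves its question unanswered.

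The source data are already in reach. Section 5 says "Patients scheduled to undergo tonsillectomy during the study period will be identified using the surgical scheduling system", and Section 6 already draws prescriptions from the chart. Section 7 has chart data entered by hand, so the cost is extra abstraction. Taking 198 as the count after exclusions, an assumed unprescribed share u adds 198/(1 − u) − 198 patients: 10.4, 22.0 or 49.5 for 5%, 10% or 20%, so about 10 to 50.

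The resulting estimate will be imprecise. For a true −20 points the 95% half-width is about 16, 19 or 24 points at an assumed 95%, 90% or 80% baseline, so it should be reported with its interval and a null read accordingly.

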 - During the month of September 2020, opioid consumption data will be reviewed by the chief of pediatric otolaryngology. A new default

- number of doses lower than 30 will be chosen based on the level and distribution of opioid consumption.
- On October 1, 2020, the tonsillectomy orderset will be changed. The new orderset will have three options for patients ≥ 12 years: one for oxycodone solution among patients < 50 kg, one for oxycodone solution among patients ≥ 50 kg, and one for oxycodone tablets. Each of these options will auto-populate the default doses field using the new setting.
 - The new orderset will display for patients at C.S. Mott Hospital only. Thus, all patients in the treatment group (patients undergoing tonsillectomy at Mott by pediatric otolaryngology attendings) will have clinicians who are exposed to the new default settings. The tonsillectomy orderset will not be changed at University Hospital, Brighton, or Livonia. Thus, all patients in the control group (patients undergoing tonsillectomy in these locations by general otolaryngology attendings) will have clinicians who will not be exposed to the new default settings, even if they use the pediatric otolaryngology tonsillectomy orderset.

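### The primary prescribing analysis drops M-POP patients, although M-POP is an option in the orderset that the intervention changes, and no planned analysis would show whether M-POP use shifts.

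*Combined protocol and SAP*

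**What the plan says.** Section 4 lists, among the exclusions for the primary analysis of prescribing, patients enrolled in the M-POP pathway, "which includes education about pain management and a small initial opioid prescription (10 doses".

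Section 6 says that pediatric otolaryngology clinicians "use a MiChart tonsillectomy orderset with three options: patients < 12 years, patients ≥12 years, and M-POP". Under the option for patients aged 12 and over, "the default is currently 30 doses, consistent with the current departmental prescribing standard".

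The same section then describes the intervention: "On October 1, 2020, the tonsillectomy orderset will be changed". A new default "number of doses lower than 30 will be chosen based on the level and distribution of opioid consumption". "The new orderset will have three options for patients ≥ 12 years", split by formulation and weight. The text does not say whether M-POP is kept, moved or removed. The new orderset is shown at Mott only; the control sites keep the existing one.

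Section 10 includes the number of doses in the discharge prescription among the primary-analysis outcomes and fits a DiD model. It has no outcome for M-POP use. Its sensitivity, subgroup and spillover analyses neither bring M-POP patients back nor compare the M-POP share by group and period.

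**The concern.** Membership of the analysed sample may depend on a choice made inside the tool that the intervention changes. There are two possible routes:

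- A default below 30 brings the standard options closer to the 10-dose M-POP prescription, so clinicians might choose M-POP less often, or more often.
- If M-POP is not carried into the new orderset, patients who would have been on it enter the post-period sample, while their pre-period counterparts stay excluded.

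Either shift would arise in the treated group after the change and not at the control sites, so the DiD contrast would not cancel it. A patient moved from 10 doses to a larger default would receive more opioid than before. That patient would nevertheless count in the post-period sample against a pre-period comparison of about 30. At stake is whether the primary estimate describes the same kind of patient before and after, and whether it can stand for all patients whose clinicians saw the new orderset.

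**Working it through.** **The plan's own figure.** Section 10 gives 113 treated and 85 control patients (198 in total) and applies 65% survey consent. 113 × 0.65 = 73.45 (plan: 74), 85 × 0.65 = 55.25 (plan: 55), 198 × 0.65 = 128.7 (plan: 129). These agree to within one patient. The plan gives no M-POP share, no count of patients removed by the exclusion, and no assumed effect size, so there is no planned effect to reproduce.

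**Inputs for an illustration**

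- From the documents: default of 30 doses on the standard option before the change; 10 doses on M-POP; new default below 30.
- Assumed: mean prescription equal to the default before the change; mean of 20 on the standard options afterwards; M-POP share before the change s = 10%, 20% or 30%; fraction of M-POP patients moving to the standard options m = 0 or 0.5; no change in the control group.

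**Planned analysis (M-POP excluded).** 20 - 30 = -10 doses, whatever s and m are.

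**All opioid-prescribed patients.** Change = [(1 - s)·20 + s·m·20 + s·(1 - m)·10] - [(1 - s)·30 + s·10] = -10 + 10s + 10sm.

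| s | no movement (m = 0) | half move (m = 0.5) | due to movement (10sm) |
|---|---|---|---|
| 10% | -9.0 | -8.5 | 0.5 |
| 20% | -8.0 | -7.0 | 1.0 |
| 30% | -7.0 | -5.5 | 1.5 |

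The term 10s is present when nobody moves. It comes only from counting patients whose dose did not change, which is a difference in target population. At m = 0.5 it makes up two-thirds of the gap from -10 (for s = 10%, 1.0 of 1.5). Movement supplies the other third.

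**Is the planned estimate itself biased?** Not in this illustration. Patients who stay on the standard options go from 30 to 20, movers also receive 20, and -10 is exactly right for non-M-POP patients. Bias needs movers to differ from stayers. Two deliberately extreme, assumed cases show the mechanism:

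- *Out of M-POP.* The share falls from 20% to 0%, movers get 20, and everyone else stays at 30. Excluding M-POP: (0.8·30 + 0.2·20) - 30 = -2.0, although no stayer changed. All patients: 28 - (0.8·30 + 0.2·10) = 28 - 26 = +2.0.
- *Into M-POP.* Before the change 30% of patients get 20 and 70% get 30 (mean 27). All of the 30% then move to M-POP. Excluding M-POP: 30 - 27 = +3.0, again with no stayer changed. All patients: (0.3·10 + 0.7·30) - 27 = 24 - 27 = -3.0.

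Selective movement can therefore even reverse the sign, but nothing in the documents indicates how likely either case is.

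**The case against.** The strongest reply is that M-POP may not be a choice at the discharge order. Section 4 speaks of patients enrolled in a pathway that includes education, and enrolment may be settled before any order is written. If so, and if it is unaffected by the new orderset, the exclusion is a pre-exposure criterion and only narrows the population. This cannot be dismissed: the documents do not say who decides enrolment, when, or on what basis. They do list M-POP as an orderset option, so the opposite cannot be dismissed either.

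It is also fair to say that excluding M-POP helps to isolate the default. M-POP bundles education with its own quantity, and including it in the primary model would credit the default with any change in M-POP uptake that arose at Mott for other reasons. This stands, and it is why the primary population should not be changed.

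A reader might infer that a shift in M-POP use will happen in the treated group. No section shows that; even the distance between the new default and 10 doses is unknown. A reader might also take the whole gap between -10 and -8.5 to -5.5 as bias. It is not: most of it exists with no movement at all.

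What the reply leaves untouched is that the exclusion relies on M-POP use being unaffected by the change, and the plan neither states nor checks this.

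**Conclusion.** The concern holds as a conditional one. If the orderset change alters M-POP use, treated patients are selected into the primary analysis differently before and after, and DiD does not remove the difference. Under assumed shares of 10-30%, half moving and a 20-dose standard option, movement changes the all-patient effect by about 0.5 to 1.5 doses, against a planned-analysis effect of -10. The planned non-M-POP estimate is biased only if movers differ from stayers. The size and direction of that bias cannot be found from the documents.

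They do not support saying that the primary result is misstated or that the exclusion is wrong. They support saying that the plan contains no analysis that would reveal the problem if it occurred.

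**What to change.** Keep the planned primary population and add the following to Sections 4, 6 and 10:

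1. State whether M-POP remains available in the new orderset, and when and by whom enrolment is decided.
2. Report M-POP use by group and period among patients who meet every other primary-analysis criterion, with a DiD estimate and confidence interval for the proportion. With about 113 treated patients over both periods, a non-significant result should not be read as proof of no shift.
3. Add a named sensitivity analysis of discharge doses that includes M-POP patients at their actual number of doses.
4. State in advance that, if the M-POP share shifts differentially, the primary estimate will be described as applying to non-M-POP patients and subject to possible selection, and not as the effect on all patients exposed to the new orderset.

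The cost is modest. Section 6 already has prescription details drawn from DataDirect and MiChart, but Section 7 has these entered by hand, so the added patients mean some extra data entry. The dose outcome will be more variable in the sensitivity analysis, and any unrelated change in M-POP uptake at Mott would also enter that result. It should therefore be read together with the M-POP share.
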